9.4.3 Exploratory endpoints

- Difference in number of emergency room visits and hospitalizations during study period between control and intervention group.
- Comparison of status of cancer (stable, progressing, in remission) between intervention and control group.

9.5 Study Schema

Figure 1:

10.0 STUDY PROCEDURES

10.1 Methods: After enrollment as above, co-investigators of this study or the assigned coordinator will be doing the consent. Patient will be randomized to intervention and control arms in a 2:1 ratio. The intervention arm will receive a dedicated workshop for one and a half hours every 2 weeks. We aim to start a 6 month long program with weekly creative writings workshops, and patient enrollment in the study will continue through the 1st 4.5 months of the 6 month period so that the last enrolled patient could complete 2 classes per month for two months. Each patient will be asked to attend at least two classes per month for a total of two months. These workshops will be held at Hershey Medical Center (HMC). At the initiation of the study along with consent we will collect baseline scores in both groups for each parameter as below. Somatic Symptom Burden (SSM-8 - Figure 2 - reference section), depression symptoms using PHQ-9 (Figure 3 – reference section), and anxiety symptoms using GAD-7 (Figure 4 – reference section) will be collected monthly and following intervention completion.

We will collect mood scores pre and post each session. We will use Emotional Thermometer Scale (EMS) from [name] (Feb. 2010), diagram for scales is shown in figure 1. Please see supplementary index for a letter of permission to use from [name]. We will give the Thermometer scales and collect scores pre and post each session and also collect scores pre and post completion of entire course. Control group will do EMS on monthly basis along with other parameters. At the end of the study we will review all participants' medical charts to count view the number of emergency room visits and hospitalizations each participant experienced during the study period. These will be further broken down in categories based on cancer

Institutional Review Board

related vs non-cancer related visits. We will also review their most current cancer disease status after completion of the workshops and categorize whether their status is considered to be stable, progressing, or in remission. Both groups will also receive follow up mood and symptom surveys twice a month for up to 2 months after completion of the participant's two to three month study period.

The control arm will receive a book (i.e., *Writing Down Bones* by Natalie Goldberg) on creative writing and asked to read and do writing activities for one and a half hours once every two weeks. At the completion of the two-month participation or completion of 4 sessions control patients will be given the opportunity to enroll in the creative writing workshops for the remainder of the study period of 6 months. We will collect scores from control arm through the same Emotion Thermometers Scale on a monthly basis. Pre-intervention scores will be obtained at the time of consent or one week prior to the planned start of session 1 for workshop (either in the clinic if possible or mail the score sheet to patients with an enclosed stamped envelope for return of the scales). Depending on participant preference, we can send them emails of the REDCAP surveys containing the same information at set intervals. A sample of the REDCAP surveys is included in supplementary materials. We will also send participants in the control arm a stamped return envelope on a monthly basis if not able to get score sheets in a clinic or over REDCAP, depending on patient convenience and preference. We will call the participants once every 3-4 weeks to check in on their progress. Please see a calendar at the end for details.

To assess for possible confounding results of patients participating in the concurrent exercise study, we will ask participants if they are also enrolled in the exercise study at enrollment and perform a subset analysis for patients who are in the exercise study. They will be randomized into either control or intervention group in the same manner as the other patients in the study. We will additionally include a section of the survey to ask about regular exercise (more than 30 minutes, three times a week) and do a subset analysis of these patients as well.

We will be collaborating with the Department of psychiatry at HMC - [name], [name], and [name]. Any subject who requests psychiatry follow up will be referred to [name]. If participants report the presence of suicidal ideation per question nine on the PHQ-9 [i.e., Thoughts that you would be better off dead or of hurting yourself in some way], they will be referred on an urgent basis to [name] or [name]. In the event [name] and/or [name] are unavailable for follow-up, If any active suicidal thoughts are reported, participants will be referred directly to Emergency Department at Hershey Medical Center.

10.2 Clinical Covariates: Detailed clinical covariates will be obtained from questionnaires and medical record review including demographics (age, gender, race), cancer type and stage, psychiatric history, chemotherapy regimen and medication use.

10.3 Creative Workshop: Write from Heart: This workshop for cancer patients usually lasts one and a half hours and is broken into several parts. Usually beginning with inspirational quotes or passages from writings of respected authors, to shift mood and illuminated deeper thought and reflection. The next phase of the class consists of sharing a beautiful or whimsical object handed person to person or placed in the middle of the table to stimulate both curiosity and the senses. When participants are able to relax fully, in tranquil and focused surroundings the imagination easily transforms a bright polished stone or a glass heart with inner fractures into a metaphorical image. The technique of journaling is also encouraged in class, as a way to promote inner awareness to strengthen writing skills and to guide students to reach for their own comfort and consolation, when not in class. Within our setting, it is normal, though not mandatory that writing may lean toward the cancer experience. At the end of each series, students would have learned how to trust their artistic instincts, connect more courageously with

Institutional Review Board

the world of their emotions and transform their fears and revelations about cancer into words on the page.

10.4 Emotional Thermometers Scale: The Emotion Thermometers tool is a simple rapid modular screening tool for detection and monitoring of emotional disorders in clinical practice. It was created by [name] J Mitchell and has a simple visual-analogue design. It is easy for most patients (including older people) to understand, quick to administer and simple to score. We have already got permission from [name] J Mitchell for royalty free usage of this scale for 2 years starting from Aug, 2016 till Aug 2018. We will be getting permission from him to extend the usage for an additional 1-2 years.

10.5 Survey of Depression and Anxiety symptoms: For anxiety, we will use Generalized Anxiety Disorder 7-item (GAD-7) validated scale by Robert Spitzer et al. For depression we will use Patient Health Questionnaire 9-item (PHQ-9) validated scale by Robert Spitzer et al. Both of these scales do not require any permission for reproduction, display, distribution or usage.

10.6 Control group activities: Participants randomized into the control group were asked to maintain their usual follow up while also reading a book on creative writing for one and a half hours every other week for three months, logging their activity for verification of task completion. Their mode scores will be measured as mentioned above.

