7.2 Accrual

We aim to accrue 60 eligible patients over a time span of 4months at the Milton S. Hershey Medical Center.

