9.2 Design

The focus of this study is to determine the difference in mental health parameters following the participation of cancer patients in a creative writing workshop. Participants will be randomized within strata formed by cancer type in order to assure that these potentially important confounding variables are balanced across groups. Patients will be enrolled on a rolling basis over a four to five-month period, allowing patients in intervention arm to participate in 2-3 months workshops (workshops would be held once every 2 weeks). Patients in control arm will be provided a book (*Writing Down Bones* by Natalie Goldberg) about creative writing and will be asked to do activities for 1.5 hours every 2 weeks. After three months, control group participants can join creative writing workshops at their discretion for the remaining period for writing workshops. Both group members will receive follow up surveys twice a month for two months at the completion of the participant's two-month study period.

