9.3 Study Duration

Estimated time to enroll all subjects = 3-5 months (Patients will start being enrolled after IRB approval and we will continue the enrollment up to 4-5 months from the time the 1st class starts for the intervention group)

Length of a participant's participation = 2 - 6 months; Follow up after participant's completion of classes = 2 months

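### Entry up to month 5 (9.2, 9.3) cannot give the last patient the two classes a month for two months that 10.1 promises, and entry at month 4.5 does so only under one reading of the class schedule

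*Combined protocol and SAP*

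**What the plan says.** All references are to the current protocol version, which stands first in the combined file.

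- **Programme and class frequency.** Section 10.1: "We aim to start a 6 month long program with weekly creative writings workshops". The same paragraph also has the intervention arm receiving one workshop per fortnight, and section 9.2 says "workshops would be held once every 2 weeks".
- **What each patient is asked to do.** Section 10.1: "Each patient will be asked to attend at least two classes per month for a total of two months". That is four classes.
- **When enrolment closes.** Section 10.1: "patient enrollment in the study will continue through the 1st 4.5 months of the 6 month period so that the last enrolled patient". The purpose it gives is that this patient still has room for two classes in each of two months. Section 9.2: "Patients will be enrolled on a rolling basis over a four to five-month period". Section 9.3: "we will continue the enrollment up to 4-5 months from the time the 1st class starts". Section 7.2: "We aim to accrue 60 eligible patients over a time span of 4months".
- **Controls.** Section 10.1 lets controls join the workshops after two months or after four sessions, for whatever is left of the six months.
- **Attendance.** Sections 4.2 and 9.4.2 relate scores to the frequency or number of classes attended. Section 9.3 puts a patient's participation at 2 to 6 months.

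The amendment letter that follows this version gives the sponsor's rule, used here as context only. The cut-off is the last day on which the requested classes can still be completed, and counting the request as two classes a month in two months allows two more weeks of enrolment.

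**The concern.** Section 10.1 gives a reason for its cut-off, and the reason can be checked. Read as elapsed time, 4.5 + 2 = 6.5 months and 5 + 2 = 7 months, against a programme that ends at month 6.

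Three things are at stake. Late workshop patients may be unable to receive the course the protocol defines. Late controls may have little or no class time left when they become free to join, which thins the secondary comparison of controls who later attend. And entry date limits how many classes a patient can attend, so an analysis on the raw number of classes mixes engagement with calendar time.

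**Working it through.** **Inputs.** Programme 6 months; cut-off 4.5 months (10.1) or up to 5 months (9.2, 9.3); four classes requested (10.1); spacing of 1 week (10.1) or 2 weeks (9.2, 10.1). Conversion: 52/12 = 4.33 weeks per month. Months are counted from the first class, as 9.3 does.

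**The plan's own figure.** The 4.5-month cut-off can be reproduced. With weekly classes, two classes are certain to fall in the rest of programme month 5 if at least two weeks of it remain. The latest such entry is 5 − 2/4.33 = 4.54 months. Two more classes then fit in month 6. So 4.5 months follows from weekly classes and from counting month 5 and month 6 as the two months. If two elapsed months are required, the latest entry is 6 − 2 = 4.0 months.

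**Classes left after entry.** Let W be the weeks left, g the spacing, and o the wait to the next class (between 0 and g). The number of classes left is floor((W − o)/g) + 1.

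| Entry at | Weeks left | Weekly | Every 2 weeks | Four classes fit, every 2 weeks |
|---|---|---|---|---|
| month 4 | 2 × 4.33 = 8.67 | 8–9 | 4–5 | always |
| month 4.5 | 1.5 × 4.33 = 6.5 | 6–7 | 3–4 | about 25% of entry dates |
| month 5 | 1 × 4.33 = 4.33 | 4–5 | 2–3 | never |

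The 25% arises because the fourth class comes 6 weeks after the first, so o must be at most 6.5 − 6 = 0.5 week out of a possible 2: 0.5/2 = 25%, with no class missed. At month 5, four weekly classes fit, but all within the single remaining month.

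**Controls (10.1 triggers).** Under the two-month trigger, entry at month 4 gives 4 + 2 = 6, so no class time remains for later entrants. Under the four-session trigger, four fortnightly sessions span 6 weeks, or 6/4.33 = 1.38 months if the first is done at entry. Entry at month 4 then qualifies at 5.38 (about 2.7 weeks left), entry at 4.5 at 5.88 (about half a week left), and entry at 5 at 6.38 (none left).

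**How many patients, and how much dilution.** These figures assume even accrual from the first class.

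- Share entering after month 4: 0.5/4.5 = 11% or 1/5 = 20%. That is about 4 to 8 of 40 workshop patients and 2 to 4 of 20 controls.
- With classes every two weeks, take the shortfall against two months as proportional to the time missing. It is 0 at month 4, 0.5/2 = 25% at month 4.5 and 1/2 = 50% at month 5, so late entrants average 12.5% or 25%.
- Overall: 11% × 12.5% = 1.4%, or 20% × 25% = 5%.

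**Attendance ceiling.** With classes every two weeks, a patient entering at the first class has 26/2 = 13 or so available. One entering at month 4.5 has 3–4, and one entering at month 5 has 2–3.

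**The case against.** The strongest reply is that the sentence in 10.1 describes weekly workshops. On that basis 6–7 classes remain at month 4.5, and two in the rest of month 5 plus two in month 6 is what the sentence promises. The amendment letter counts classes in the same way. This stands: a reader might infer that nobody entering at month 4.5 can complete the course, and the documents do not support that. The defence does need both weekly classes and calendar counting, and 9.2 and the other sentence of 10.1 contradict the first. It does not rescue month 5, and the two extra weeks argued for in the letter lead from the previous 4-month cut-off to 4.5 months, not to 5.

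Other stronger readings also fail:

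- *The offer to controls is empty after month 4.* Not for all of them. The four-session trigger can leave a short remainder. (Sections 9.2 and 11.1 give later joining times of three months and week 12; that is a separate inconsistency.)
- *Late patients' outcome is measured at the wrong time.* This is weak. Section 9.4.1 ties the final mood score to completion of sessions and accepts that this varies, and 10.1 also collects PHQ-9 and GAD-7 after completion.
- *The plan has four conflicting windows.* This is too strong. Sections 9.2 and 9.3 agree, 4.5 lies within their range, 7.2 is an accrual aim, and the 3–5 months in 9.3 is an estimate of time to enrol.
- *The late cut-off is what distorts the attendance analysis.* Only in part. With participation of 2 to 6 months, entry date would cap attendance even if entry closed at month 4.

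The schema and the calendar that 10.1 refers to cannot be read in the available text and may settle the class frequency.

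**Conclusion.** The allowance up to month 5 in 9.2 and 9.3 is incompatible with the promise in 10.1, at either class frequency. The 4.5-month cut-off is compatible under weekly classes and calendar months. Under classes every two weeks it usually leaves three of the four classes, and two full elapsed months never fit after month 4. Controls entering after month 4 have no class time left under the two-month trigger and at most about 2.7 weeks under the four-session trigger.

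A reader might infer that the main comparison is materially diluted. It is not: the expected loss is about 1% to 5% of classes on average. That range rests on even accrual from the first class and on classes every two weeks. Enrolment before the first class, which 9.3 permits, would lower it. The clearer statistical consequence is for the attendance objective, where the raw class count depends on entry date.

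**What to change.** 1. State one last-enrolment date in 7.2, 9.2, 9.3 and 10.1, derived from the actual class calendar so that the property claimed in 10.1 is true. Remove the allowance up to month 5 if the calendar does not support it.
2. Reconcile the weekly and every-two-weeks statements in 9.2 and 10.1, and say whether two months means elapsed or calendar time.
3. For the attendance objective, analyse the share of available classes attended in the first two months, or adjust for the number of classes available.

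The first two items are wording and the third is a line in the analysis plan. The one real cost is accrual: closing entry at 4.5 rather than 5 months gives up as much as half a month. The only rate in the documents is 15 patients in a month and a half, reported in the earlier amendment letter before eligibility was widened. At that rate (15/1.5 = 10 per month) the cost is about 0.5 × 10 = 5 patients.

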9.4 Endpoints:**9.4.1 Primary endpoints:**

- Mood scores before (at baseline) and after intervention (after completion of entire sessions - this may vary as some patients may not be able to complete six sessions). A validated Emotional Thermometer Scales will be used to predict changes in parameters pre and post-intervention.
- Severity of depression and anxiety symptoms before and after intervention between two groups. Validated Depression and Anxiety questionnaires will be used to predict changes, the PHQ-9 and GAD-7 respectively.

9.4.2 Secondary endpoints:

[figure not shown]
- Mood and symptoms before and after at least 2 sessions of intervention.
- Self-reported somatic symptoms pre and post intervention in two groups. We will use the Somatic Symptom Scale – 8 (SSM-8) to quantify somatic symptom burden.
- Difference in scores and symptoms between various genders.
- Difference in scores and symptoms between patients living alone versus with family.
- Difference in scores and symptoms in different cancer types.
- Difference in scores and symptoms versus number of classes attended.
- Differences between individual mood scores for patients in the control group who later switch to intervention group and attend at least one session
- Mood and symptom scores up to 2 months after completion of the study.

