11.0 Statistical Plan

11.1 Statistical Analysis Plan

Participants' basic demographic and baseline clinical measurements will be summarized using descriptive statistics. Those summarizations will be based on all patients as well as on patients within each group. This study has several main groups of outcome variables, which reflect several different domains of patient's mental health. The first group is the emotion thermometer (which has five sub-scales), the second is the somatic symptom scale (SSS-8), the third is the Patient Health Questionnaire (PHQ-9), and the fourth is the Generalized Anxiety Disorder questionnaire (GAD-7), which measures participants' anxiety. All the above outcome variable groups are based on questionnaires using Likert-scale questions to take the measurements, and each group may involve multiple sub-dimensions. Both the intervention group and the control group have repeated measures of the outcomes as shown in Figure 1. Graphical methods (such as the line plot of mean/SD values vs. time) will first be used to illustrate the mean and standard deviation values of the mode, depression, and anxiety scores through the time for both groups. These methods will help us detect the patterns of how the scores change over time (within-group change) and how the scores differ between groups. We will further use the linear mixed-effect model for repeated measures to analyze the within-group and between-group differences. Every sub-dimension will be analyzed individually, but we will also analyze the composite score for the dimensions. For the patients in the control group this study involves two stages (week 1-12 and week 13-20), and at the end of the 12th week, they can join the intervention group. This setting will allow us to study the effect of the intervention on the control group alone. For this part of analyses, linear mixed-effect models will be set up with the stage serves as an indicator variable in the model. The comparison of outcome variables between certain time points will also be done using paired tests. We will further investigate the possible factors that might affect the change of outcome variables over time. The factors are gender, race, marital status, time from cancer diagnosis (first 3 months, 3-6 months, more than 6 months) and cancer stages. This part of analyses will mainly be focused on the intervention group and the above factors will be examined in the linear mixed-effect models. All analyses will be performed using statistical software SAS version 9.4 or higher (SAS Institute, Cary, NC, USA) and the statistical significance level to be used is 0.05.

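### Thermometer scores are class-linked in the workshop arm and monthly in controls; if post-class scores enter the between-arm model, a short-lived drop favours the workshop

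*Combined protocol and SAP*

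**What the plan says.** For the thermometer in the workshop arm, 10.1 will "collect scores pre and post each session and also collect scores pre and post completion of entire course". For the other arm, "Control group will do EMS on monthly basis along with other parameters". PHQ-9, GAD-7 and SSS-8 follow one rule, with no class-linked scoring: they "will be collected monthly and following intervention completion".

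The first primary endpoint (9.4.1) is the mood score at baseline and "after completion of entire sessions - this may vary as some patients may not be able to complete six sessions". No day or place is given for the later score.

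For the analysis, 11.1 states: "We will further use the linear mixed-effect model for repeated measures to analyze the within-group and between-group differences". On which measurements, it says: "Both the intervention group and the control group have repeated measures of the outcomes as shown in Figure 1". That schema is not reproduced in the text available here. Nor is the schedule to which 10.1 refers: "Please see a calendar at the end for details". The text of 11.1 does not say whether pre-class, post-class, monthly or end-of-course scores enter. Section 11.2 assumes four time-points without naming them.

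Two other sources of scores matter. Section 10.1 offers electronic forms: "Depending on participant preference, we can send them emails of the REDCAP surveys containing the same information at set intervals". Sections 9.2 and 10.1 also give both arms follow-up surveys twice a month for two months after the participation period; 9.4.2 treats these scores as secondary.

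**The concern.** Controls have no class, so none of their scores can be a post-class score. A workshop patient who attends the four requested classes gives up to eight class-linked scores, four of them straight after a class. A control gives about two monthly scores in the same two months. The only in-course thermometer scores that the text clearly schedules for the workshop arm are class-linked.

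The pilot in 5.2 found lower scores after class than before it at each visit, and lower is better on this scale. If such scores enter the comparison of arms, the contrast mixes any effect that outlasts the class with the moment of measurement, in the workshop's favour. A repeated-measures model fitted to everything recorded would include them. What is at stake is the first primary endpoint only.

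**Working it through.** **Inputs.** From 11.2: 40 versus 20 patients, effect 0.45 SD, four time-points, autocorrelation 0.2. From 11.1: level 0.05; two-sided is my assumption. From 10.1: two classes a month for two months, so 8 session scores (4 post-class) against 2 monthly control scores. Post-class drop d: not in the documents; assumed 0.1, 0.2, 0.3 and 0.5 SD. Outcome SD is 1 throughout, and there is no effect beyond the drop.

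**1. The plan's own power.** Under AR(1) with rho 0.2, the variance of a mean of four scores is [4 + 2(3×0.2 + 2×0.04 + 0.008)]/16 = 0.336. SE = sqrt(0.336 × (1/40 + 1/20)) = 0.159. Power at 0.45 SD is 80.9% (normal) or 79.6% (t, 58 df), which reproduces the stated 80%. Under compound symmetry the variance is 0.40 and power is 73.8% (normal), so 11.2 evidently assumes AR(1).

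**2. No post-class score analysed.** The bias is zero.

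**3. All session scores pooled.** Half the workshop scores carry the drop, so the bias is d/2: 0.05, 0.10, 0.15 and 0.25 SD, or 11, 22, 33 and 56% of 0.45. With equal correlation 0.2, the variance of a patient's mean is (1 + 7×0.2)/8 = 0.30 in the workshop arm and (1 + 0.2)/2 = 0.60 in controls. SE = sqrt(0.30/40 + 0.60/20) = 0.194. The rejection rate is Φ(bias/SE − 1.96) + Φ(−bias/SE − 1.96).

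**4. The same, with four follow-up surveys per arm added.** There are now 12 scores against 6, so the bias is d/3. SE = sqrt(0.267/40 + 0.333/20) = 0.153.

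**5. The only final score is the last post-class sheet.** The bias is d and SE = sqrt(1/40 + 1/20) = 0.274. As a change from baseline at rho 0.2, SE is 0.274 × sqrt(1.6) = 0.346. Both use the noncentral t with 58 df.

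| Reading | d = 0.1 | 0.2 | 0.3 | 0.5 |
|---|---|---|---|---|
| 8 v 2, rho 0.2 | 5.8% | 8.1% | 12.1% | 25.2% |
| 8 v 2, rho 0.5 | 5.6% | 7.2% | 10.1% | 19.6% |
| 12 v 6, rho 0.2 | 5.6% | 7.2% | 10.0% | 19.4% |
| 12 v 6, rho 0.5 | 5.3% | 6.2% | 7.7% | 12.7% |
| Final post-class sheet | 6.5% | 11.1% | 19.0% | 43.5% |
| Same, change from baseline | 5.9% | 8.8% | 13.6% | 29.5% |

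The normal approximation gives 44.7% for the 43.5% cell. A simulated random-intercept fit of the 8 v 2 case at rho 0.2 (10,000 runs per cell) gives 7.6, 11.0 and 23.4% for drops of 0.2, 0.3 and 0.5. With a shared baseline and an arm-by-period contrast it gives 5.8, 7.5 and 11.9%.

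**6. Power with matched scores only.** At 0.45 SD, AR(1) rho 0.2, t with 58 df:

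| Matched scores | Variance of mean | Power | Detectable at 80% |
|---|---|---|---|
| 2 | 0.600 | 55.0% | 0.60 SD |
| 3 | 0.431 | 69.2% | 0.51 SD |
| 4 | 0.336 | 79.6% | 0.45 SD |

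**The case against.** The best defence is that the endpoint is already defined away from the classes. Section 9.4.1 compares baseline with the end of the course, and the word also in 10.1 suggests that the course-level pair is separate from the session sheets. On that reading the session scores are extra data and the bias is zero, unless the course-level form is filled in straight after the last class, which no passage says. This stands. It is why the point is conditional, and why a reader should not infer that the primary endpoint is biased as written.

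Second, Figure 1 and the calendar may list the collection times. This stands too: the documents do not support saying that the plan has no schedule, only that the available text of 11.1 does not exclude post-class scores.

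Third, the size is assumed. The pilot gives a direction only, from 11 workshop patients with weekly two-hour classes. The scale asks about the past week including today, so one class may move it little, and at 0.1 SD the error rate is close to nominal.

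Fourth, matched follow-up surveys exist in both arms and would dilute the bias if pooled (row 12 v 6). They cannot replace the in-course contrast: they are secondary, and controls may have joined workshops by then.

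It may also be said that one sentence in 11.1 is enough. That holds only if an off-class in-course score already exists for the workshop arm.

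**Conclusion.** The point holds conditionally. The thermometer schedules differ by arm, and the text of 11.1 does not keep post-class scores out of the between-arm model. If they enter, the bias runs towards the workshop. With no lasting effect and assumed drops of 0.1 to 0.5 SD, rejection is about 6 to 25% when session scores are pooled at rho 0.2, lower with a shared baseline or the follow-up surveys, and 6.5 to 44% when the only final score is a post-class sheet. If none enters, the bias is zero.

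Two stronger inferences fail. One is that both primary endpoints are affected: PHQ-9 and GAD-7 are collected monthly with no scoring around classes. The other is to treat every workshop score as post-class, which would give far larger error rates: 10.1 collects a pre-class score for each post-class one.

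This should be settled before analysis, because a choice of scores made after seeing the data would not be credible.

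**What to change.** First check Figure 1, the calendar and the REDCap surveys for thermometer scores that the workshop arm completes away from class.

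Then state in 9.4.1 and 11.1 that the between-arm thermometer contrast uses baseline and named times from randomisation common to both arms. State also that post-class scores are excluded from it and reported only as a description within the workshop arm. Pre-class scores alone are a weaker substitute: they exist only for sessions attended and do not fall at the control times.

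Only if no off-class in-course score exists, add the thermometer to the workshop arm's existing monthly PHQ-9, GAD-7 and SSS-8 survey and have it completed away from class. Keep the twice-monthly follow-up surveys as secondary.

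Name the time-points behind 11.2, and restate its power if fewer than four are matched.

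The minimum cost is a sentence in each of 9.4.1 and 11.1. The most is one short extra scale a month. The price is fewer scores in the between-arm test: at 0.45 SD, power is about 55% with two matched scores and 69% with three, against 80% with four.
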